6.4.3 EXCLUDED CONCOMITANT MEDICATIONS

Other investigational agents should not be used during the study.

7 STUDY TESTS AND OBSERVATIONS

Protocol-required tests, observations, and procedures are summarized in the Schedule of Events, [Appendix A](#).

Safety Measures

A CBC including platelets and basic metabolic chemistry panel (eg, Chem 7 or 8) will be performed on Day 1 of each cycle. Other general safety monitoring (eg, physical examinations, imaging, specialty tests, etc.) shall be in accordance with institutional guidelines and as clinically indicated. These data will not be routinely recorded on case report forms (CRFs).

Pregnancy Test

Females of Child Bearing Potential (FCBP) must have a negative serum or urine pregnancy test, with a sensitivity of at least 50 mIU/mL within 3 days prior to dosing. All subjects must be informed that he/ she needs to use a dual effective method of birth control while in this study, such as oral contraceptives plus use of a physical barrier (ie, condom) for the full duration of the study, plus 3 additional months.

7.1 SCREENING (DAYS –30 TO –1)

The following screening assessments must be performed between Days –30 and –1:

1. Obtain written informed consent prior to carrying out any study procedure
2. Obtain previous PX-171 protocol unique identifier (patient study number)
3. Determine eligibility according to Inclusion/Exclusion criteria (see [Section 4](#))
4. Perform Disease Assessments, ie, extent of disease measurements (per method employed in previous protocol); and response category (see [Appendix D–E](#)).
Note: If disease assessments are performed previously within 30 days of first dose of extended carfilzomib therapy study drug, a second disease assessment will not be required.
5. Perform routine physical examination
6. Perform pregnancy test for FCBP
7. Obtain height, weight, and BSA
8. Obtain Eastern Cooperative Oncology Group (ECOG) performance status and neuropathy grade
9. OPTIONAL: Bone marrow aspirate and/or biopsy sample collection for cytogenetic and fluorescent in situ hybridization (FISH) analysis (only for *MM* subjects whose disease status at study entry is PR, MR or SD).
10. Record peripheral neuropathy AEs (all grades)
11. Record Grade 3 and 4 AEs, and all SAEs

12. Record AE (any Grade) leading to a missed carfilzomib dose, carfilzomib dose reduction or discontinuation.
13. Record any concomitant chemotherapy agents

7.2 CYCLE 1 (DAY 1)

The following assessments must be completed on Cycle 1, Day 1:

1. Serum chemistry – basic chemistry panel (Chem 7 or 8), pre-dose. Laboratory values may be obtained within 24 hours prior to treatment for convenience. Results must be reviewed prior to dosing.
2. CBC and platelet count – pre-dose. Laboratory values may be obtained within 24 hours prior to treatment for convenience. Results must be reviewed prior to dosing.
3. *Administer carfilzomib dose IV*
4. Record peripheral neuropathy AEs (all grades)
5. Record Grade 3 and 4 AEs, and all SAEs
6. Record AE (any Grade) leading to a missed carfilzomib dose, carfilzomib dose reduction, or discontinuation. In the event of a toxicity leading to a dose reduction or discontinuation, pertinent laboratory measurements and concomitant medications will be collected and monitored as unscheduled visits
7. Record any concomitant chemotherapy agents

7.3 CYCLE 1 (DAYS 2, 8, 9, 15, AND 16)

The following assessments must be completed on Cycle 1 on Days 2, 8, 9, 15, and 16 (or the same dose level and frequency as administered at the last visit of the prior carfilzomib study):

1. *Administer carfilzomib dose IV*
2. Record peripheral neuropathy AEs (all grades)
3. Record Grade 3 and 4 AEs, and all SAEs
4. Record AE (any Grade) leading to a missed carfilzomib dose, carfilzomib dose reduction, or discontinuation. In the event of a toxicity leading to a dose reduction or discontinuation, pertinent laboratory measurements and concomitant medications will be collected and monitored as unscheduled visits.
5. Record any concomitant chemotherapy agents

7.4 CYCLES 2 AND HIGHER (DAY 1)

The following assessments must be completed on Cycle 2 and higher (Day 1):

1. Serum chemistry – basic panel (Chem 7 or 8), pre-dose; laboratory values must be reviewed prior to dosing.
2. CBC and platelet count, pre-dose; laboratory values must be reviewed prior to dosing.

3. Obtain weight and BSA
4. *Administer carfilzomib dose IV*
5. Record peripheral neuropathy AEs (all grades)
6. Record Grade 3 and 4 AEs, and all SAEs
7. Record AE (any Grade) leading to a missed carfilzomib dose, carfilzomib dose reduction, or discontinuation. In the event of a toxicity leading to a dose reduction or discontinuation, pertinent laboratory measurements and concomitant medications will be collected and monitored as unscheduled visits.
8. Record any concomitant chemotherapy agents

7.5 CYCLES 2 AND HIGHER (DAYS 2, 8, 9, 15, AND 16)

The following assessments must be completed on Cycle 2 and higher on Days 2, 8, 9, 15, and 16 (or the same dose level and frequency as administered at the last visit of the prior carfilzomib study):

1. *Administer carfilzomib dose IV*
2. Record peripheral neuropathy AEs (all grades)
3. Record Grade 3 and 4 AEs, and all SAEs
4. Record AE (any Grade) leading to a missed carfilzomib dose, carfilzomib dose reduction, or discontinuation. In the event of a toxicity leading to a dose reduction or discontinuation, pertinent laboratory measurements and concomitant medications will be collected and monitored as unscheduled visits.
5. Record any concomitant chemotherapy agents

7.6 CYCLE 3 AND EVERY 3 CYCLES (DAY 1)

The following assessments must be completed on Cycle 3 and every 3 cycles (Day 1):

1. Serum chemistry – basic panel (Chem 7 or 8), pre-dose; laboratory values must be reviewed prior to dosing.
2. CBC and platelet count, pre-dose; laboratory values must be reviewed prior to dosing.
3. Perform Disease Assessments, ie, extent of disease measurements (per method employed in previous protocol); and response category (see [Appendix D–E](#)).
Note: If disease assessments, per standard institutional practices, occur more frequently than every 3 months (eg every month or every 2 months), the most recent assessment may be reported.
4. *Administer carfilzomib dose IV*
5. Record peripheral neuropathy AEs (all grades)

6. Record Grade 3 and 4 AEs, and all SAEs
7. Record AE (any Grade) leading to a missed carfilzomib dose, carfilzomib dose reduction, or discontinuation. In the event of a toxicity leading to a dose reduction or discontinuation, pertinent laboratory measurements and concomitant medications will be collected and monitored as unscheduled visits.
8. Record any concomitant chemotherapy agents

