5 SUBJECT ENROLLMENT

The screening period for a particular subject commences at the point which the subject signs the informed consent. Consent must be signed before any study-specific tests may be performed.

Subject demographics, including previous carfilzomib study unique identifier, will be captured in a study enrollment form. Tumor measurements and efficacy assessments (eg, extent of disease measurements and objective response category) relevant to the subject's tumor type will be collected in accordance to the method(s) employed in the subject's previous carfilzomib study protocol. Refer to [Appendix D–E](#) for Response Criteria. For subjects participating in a carfilzomib trial without explicit tumor measurements and defined response criteria (eg, PX-171-008), response to treatment will be tabulated using the appropriate method (eg, RECIST criteria for solid tumors). Response to treatment will be based on the tumor assessment conducted at the time of screening for the current study. Disease assessments will be required within 30 days prior to study enrollment, at least every 3 months throughout the extended treatment period (Day 1), and at end of study visit.

After a subject has been screened and has successfully fulfilled all eligibility criteria, the site representative will fax the inclusion/exclusion checklist and all other required documentation to Onyx Therapeutics.

Subjects will retain their study-specific number from the previous study. This number will be used to identify the subject throughout the study and must be used on all study documentation related to that subject.

The number of subjects may be expanded to include eligible subjects from future studies, to further establish safety and efficacy, if needed.

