6.2.3 DOSE MODIFICATIONS FOR NON-HEMATOLOGIC TOXICITIES

Study drug should be held for drug-related \geq Grade 3 events until resolution to \leq Grade 1 or return to baseline status. For the purposes of this study, ‘baseline’ refers to the subject’s status at the start of this Protocol (PX-171-010).

After resolution to \leq Grade 1 or return to baseline status of the event, subsequent treatment with carfilzomib may resume at full dose at the Investigator’s discretion.

If required by continued or worsening toxicity, dose level and/or frequency reductions will be permitted after discussion with the Medical Monitor. The minimum dose level will be 11 mg/m². Dose reductions below 11 mg/m² will not be permitted. The minimum dose frequency will be carfilzomib administration on Days 1, 2, 15, and 16 (eg, every other week). Less frequent dosing will not be permitted. If the toxicity continues, the subject should be removed from the study.

For subjects whose dose level/frequency is reduced due to study drug-related toxicity, dose level/frequency re-escalation may be considered if the subject tolerates the reduced regimen and at the Investigator's discretion in consultation with the Medical Monitor.

If there is no resolution of toxicity after 2 weeks of withholding treatment (up to 3 weeks for infection treatment), the subject will be withdrawn from the study.

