6.2.3.4 Conditions Not Requiring Dose Reduction

The following conditions are exceptions to the above guidelines. Carfilzomib does not need to be held in the following cases:

- Grade 3 nausea, vomiting, or diarrhea (unless persisting > 3 days with adequate treatment of anti-emetics or anti-diarrheals)
- Grade 3 fatigue (unless persisting for > 14 days)
- Alopecia
- \geq Grade 3 hyperglycemia attributed to dexamethasone

Other exceptions may be discussed with the Medical Monitor on a case-by-case basis.

6.2.4 *MISSED DOSES*

Missed doses will not be replaced during a cycle. If a subject misses greater than 2 doses of any cycle for reasons other than toxicity, the subject will be discontinued.

6.2.5 *CHANGES IN BODY SURFACE AREA*

Dose adjustments do not need to be made for weight gains/losses of $\leq 20\%$. Subjects with a BSA of $> 2.2 \text{ m}^2$ will receive carfilzomib based on 2.2 m^2 BSA.

6.2.6 *OTHER DOSING MODIFICATIONS*

Dose modifications and delays different from those stated in the protocol, for management of toxicities, may be permitted but must be decided jointly by the Principal Investigator and the Medical Monitor or designee.

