7.8 TUMOR RESPONSE ASSESSMENT

Efficacy Measures

Tumor measurements and efficacy assessments will be in accordance with the methods employed in the subject's prior carfilzomib study. For subjects participating in a carfilzomib trial without prior tumor measurements and efficacy assessments (eg, PX-171-008), tumor assessments will be conducted at the time of screening for the current study using the appropriate method (eg, RECIST criteria for solid tumors); these assessments will be used as the subjects' baseline disease assessments for determining response and progression while on the current Protocol (PX-171-010). Disease assessments (eg, Extent of Disease Measurements and objective response category) will occur within 30 days prior to enrollment to determine eligibility, at least every 3 months throughout study participation, and at end of study. Subjects will be evaluated for disease response according to the parameters employed in their previous carfilzomib study. Refer to [Appendix D–E](#) for Response Criteria.

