5.2 Study Day

Study Day represents the elapsed number of days from Study Day 1, inclusive. Unless otherwise specified, the timing of all study-related events, assessments, and interventions will be calculated relative to Study Day 1. If assessment date is after date of study day 1, study day will be calculated as:

$$\text{Study Day } n = (\text{Date of assessment} - \text{Date of Study Day 1}) + 1 \text{ day}$$

If assessment date is before date of study day 1, study day will be calculated as:

$$\text{Study Day } -n = \text{Date of assessment} - \text{Date of Study Day 1}$$

5.3 Cycle 1 / Cycle Day 1

The first 28-day treatment cycle will begin with the first dose of carfilzomib, and will be denoted as “Cycle 1 / Cycle Day 1”. In general, the start date of each cycle (i.e., Cycle Day 1 of Cycle k , where $k=1$ to last cycle) equals the date of the first dose of carfilzomib administered in the corresponding cycle. If carfilzomib is permanently discontinued,

then the cycle and cycle day for study-related assessments done after the last cycle of carfilzomib will be replaced in the tables, figures, and listings with the visit label (e.g., end of study assessment). The visit date and study day also will be used to identify the timing of such assessments.

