7.7.2 Progression Free Survival (PFS)

PFS is defined as number of days between start of treatment and first evidence of documented disease progression or death (due to any cause), whichever occurs first. Disease progression will be determined by the local investigator for regimens with the same baseline using the International Uniform Response Criteria ([Durie et al. 2006, with corrections](#)) (IMWG-URC) for multiple myeloma subjects and RECIST criteria ([Therasse et al. 2000](#)) for solid tumor subjects. PFS will be re-calculated whenever the baseline is reset due to addition of new anti-cancer therapy or increase of carfilzomib dose/frequency:

- 1) For regimens that continue from initial study without baseline being reset, if subjects didn't progress before PX-171-010, then PFS for the period from initial study to PX-171-010 study will be calculated as Disease Progression /Death Date – Date of first dose in initial study + 1 day, and PFS for the period of PX-171-010 study only will be calculated as Disease Progression /Death Date – Date of first dose in PX-171-010 + 1 day.
- 2) For regimens that start in PX-171-010 study with baseline being reset from initial study or previous regimens, PFS will be calculated as Disease Progression /Death Date –

Date of first dose in the first regimen among the regimens with common baseline + 1 day.

PFS will be right-censored for subjects who met one of the following conditions: 1) no baseline disease assessments or any post-baseline assessments, 2) alive and does not have documentation of disease progression before a data analysis cutoff date. The PFS censoring rules are described in Table 1.

Table 1. Censoring Rules for PFS Analysis

Situation	Date of Progression or Censoring	Outcome
No baseline disease assessments or any post-baseline assessments	Date of first dose	Censored
Alive and without documentation of disease progression	Date of last disease assessment	Censored
Death or disease progression between planned disease assessments	Date of death or first disease assessment showing disease progression, whichever occurs first	Progressed
Death or PD immediately after more than 1 consecutively missed disease assessment visit*	Date of last disease assessment before the first missed visit	Censored
Death before first disease assessment	Date of death	Progressed

* If death or PD is more than 168 days after previous disease assessment, or the first dosing date if there is no previous disease assessment.

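### Disease assessments follow the cycle count while a separate 3-month minimum also applies, and nothing says which governs when a Day 1 slips; the SAP's 168-day censoring limit leaves no room for such a slip

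*Protocol*

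**What the plan says.** **Cycle rule.** Protocol Section 7.6 states: "The following assessments must be completed on Cycle 3 and every 3 cycles (Day 1", and disease assessment is on its list. Appendix A shows the same timing.

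**Calendar rule.** Section 7.8 asks for disease assessment "at least every 3 months throughout study participation, and at end of study". The Synopsis says the same. Section 5 repeats the 3-month minimum and attaches it to a Day 1.

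**What starts a cycle.** SAP Section 5.3 uses 28-day cycles and says that, in general, a cycle's start date "equals the date of the first dose of carfilzomib administered in the corresponding cycle".

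**Holds.** Protocol Sections 6.2.2 and 6.2.3 withdraw a subject whose toxicity has not resolved after 2 weeks of withheld treatment, or up to 3 weeks for infection treatment. Section 6.2.4 adds: "Missed doses will not be replaced during a cycle".

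**Censoring.** SAP Table 1 (Section 7.7.2) censors PFS when death or progression follows more than one consecutively missed assessment. Its footnote makes this operational: "If death or PD is more than 168 days after previous disease assessment". Section 7.7.3 applies the same rules to TTP, except for death.

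Neither document says which timing rule prevails when a cycle starts late, and neither gives a window for the assessment visit.

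**The concern.** In PFS and TTP, progression found at a visit is dated at that visit. If the visit moves with the dosing calendar, the dating of progression depends in part on how well the subject tolerates treatment: a subject whose Day 1 is held is looked at later. With no control arm, the Kaplan-Meier quartiles by cohort and regimen are themselves the reported result, so nothing shares or cancels the shift.

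The censoring limit raises a second issue. If it is set to the undelayed schedule with no tolerance, a subject with one missed visit and a slight delay can lose a real event, which becomes a censored observation dated back to the last assessment before the gap.

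**Working it through.** **Inputs**
- Cycle length 28 days; a cycle starts at its first dose given (SAP 5.3).
- Visits on Day 1 of Cycles 3, 6, 9 and so on (Protocol 7.6, Appendix A).
- Longest hold before withdrawal: 14 days, or 21 for infection (Protocol 6.2.2, 6.2.3, 6.2.3.2).
- Censoring limit 168 days (SAP Table 1 footnote).
- Assumption: three calendar months are 89 to 92 days, mean 365.25/4 = 91.3.
- Assumption: missed mid-cycle doses leave the cycle calendar in place, since they are not replaced.

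**1. The plan's own figure.** 3 × 28 = 84 days, and 2 × 84 = 168. The footnote is exactly two undelayed cycle-based intervals. Two 3-month intervals would be 2 × 91.3 = 182.6, about 183 days.

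**2. Slack between the two rules.** 89 − 84 = 5; 91.3 − 84 = 7.3; 92 − 84 = 8. The rules are compatible for delays up to about a week. The first interval is tighter: screening at Day −30 to an undelayed Cycle 3 Day 1 is 30 + 56 = 86 days, leaving 3 to 6.

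**3. Which holds move the next Day 1.** For a hold of H days starting on cycle day s, delay = max(0, s + H − 29) and interval = 84 + delay.

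| Hold starts | 14 days: delay / interval | 21 days: delay / interval |
|---|---|---|
| Day 2 | 0 / 84 | 0 / 84 |
| Day 8 | 0 / 84 | 0 / 84 |
| Day 9 | 0 / 84 | 1 / 85 |
| Day 15 | 0 / 84 | 7 / 91 |
| Day 16 | 1 / 85 | 8 / 92 |
| Next Day 1 (Day 29) | 14 / 98 | 21 / 105 |

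A 7-day hold over Day 1 gives 91 days, which is borderline. Any Day 1 delay of 9 days or more gives at least 93, over every 3-month span.

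**4. Detection lag.** If progression is uniform within an interval, the mean wait to the next visit is half the interval: 84/2 = 42, 98/2 = 49, 105/2 = 52.5. The extra lag in an affected interval averages 7 or 10.5 days, and no single progression is dated more than 14 or 21 days later.

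**5. Effect over a whole cohort.** A simulation used exponential progression times with assumed true medians of 6, 9 and 12 months and gave every subject one hold before the Cycle 6 visit. Mean detected time rose by 1.1 to 1.9 days for a 14-day hold and 1.8 to 3.1 days for a 21-day hold. The detected median moved by the full 14 or 21 days, because detected times fall on visit dates and all later visits shift. That is an upper case: it needs the delay in everyone.

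**6. The censoring limit.** One missed visit plus one day of delay: 84 + 84 + 1 = 169 > 168. With a 14-day or 21-day delay: 182 or 189. One missed visit on a 3-month calendar: about 183. All are censored as if more than one visit had been missed.

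**The case against.** The other side has several good points.

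- The 3-month minimum stands on its own. A site can meet both rules by adding an assessment when a cycle slips, and a site that does not is out of compliance with Section 7.8. True, but the Schedule of Events does not prompt it, and Section 5 ties the minimum to a Day 1, which cannot be met during a long Day 1 hold.
- The cycle-start sentence in SAP 5.3 is qualified and may be only a labelling convention; the protocol does not say that a held Day 1 moves the visit. This stands as an ambiguity and is a reason to settle the matter.
- Other provisions limit the lag. Section 7.6 and Appendix A let more frequent local assessments be reported. Section 8 dates progression, for subjects withdrawn for it, by the test or procedure that showed it. Section 7.7 requires an assessment within 30 days of the last dose. These reduce the effect, though the first is optional and the last helps only those who stop.
- The study is single-arm, tests no hypothesis and has safety as its primary endpoint. So there is no between-arm bias and no error rate at risk.

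A reader might go further and infer that any single toxicity hold breaks the 3-month rule. The table in the working shows otherwise: most mid-cycle holds leave the next Day 1 in place. A reader might also size the effect from a maximum hold before each of three successive cycles: 84 + 42 = 126 or 84 + 63 = 147 days, hence 21 or 31.5 extra days of mean lag. That is an extreme case, and Sections 6.2.2 and 6.2.3 say that subjects whose toxicity continues despite reductions should be removed. Nor does the 168-day limit rest on three calendar months; it matches the undelayed cycle schedule.

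**Conclusion.** The point holds in a limited form. Two timing rules coexist with 5 to 8 days of slack, while holds of 14 to 21 days are tolerated and no order of precedence is given. A breach requires Day 1 itself to slip by more than about a week, and a site that relies on the cycle schedule alone. The resulting upward shift in PFS and TTP is modest. It rests on uniform progression within an interval and on no interim local assessment. How many subjects would be affected cannot be derived from the documents.

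The zero tolerance in the 168-day limit is the firmer part, because it follows from arithmetic alone: a single missed visit with any delay meets a rule meant for more than one. Delay alone does not trigger it; a missed visit is needed as well.

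**What to change.** **Protocol** (Synopsis, Sections 5, 7.6 and 7.8, Appendix A): schedule disease assessment at Week 8 and every 12 weeks thereafter, counted from PX-171-010 Cycle 1 Day 1, regardless of dose delays or cycle number. This reproduces the undelayed visits on study Days 57, 141 and 225.

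State a visit window and make it agree with the maximum interval. With ±w days, two visits can be 84 + 2w days apart. A ±7-day window allows 98 days, so it must go with replacing the 3-month minimum by 12 weeks ±7 days. If the 3-month wording stays, use a narrower window: ±3 days allows 90, which exceeds only the shortest (89-day) 3-month span, and ±2 days allows 88, which clears all of them.

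**SAP Table 1:** define a missed visit against that calendar, and set the footnote to two intervals plus the windows: 168 + 14 = 182 days with ±7, or 168 + 6 = 174 with ±3.

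**Cost:** wording changes, and some assessments will fall away from a dosing Day 1. Subjects without delays see no change in schedule. No dose or hold rule is affected.
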